## 2021-P-000961 Detailed Protocol

### I. BACKGROUND AND SIGNIFICANCE

This project is designed to test for the first time whether glucose metabolism is differentially impaired by sleep restriction with and without additional exposure to artificial light at night (ALAN). Laboratory studies have shown that sleep restriction to 4-6h per night for durations varying from one to 14 days reduces glucose tolerance in otherwise healthy adults [10-23,32,33], but the mechanisms by which insufficient sleep impairs glucose metabolism are still unknown. Current theories are based on the premise that the adverse metabolic consequences are caused by reduction in the duration of sleep *per se* [34]. However, sleep curtailment is typically accompanied by longer exposure to artificial light at night (ALAN), which is an environmental endocrine disrupter that profoundly disrupts circadian rhythms [24-27,35-37].

We have previously reported that acute circadian misalignment induced hyperglycemia comparable to pre-diabetic states in a third of otherwise healthy participants [55]. Since then, we have shown that even when the circadian phase of participants was realigned, prior exposure to 2 ½ weeks of chronic sleep restriction combined with a history of recurrent circadian disruption induced even more deleterious effects on glucose metabolism [32], in which pancreatic beta cells failed to respond adequately to increased glucose levels. Moreover, both night and rotating shift work (which induce circadian disruption) are associated with increased risk for metabolic problems (81)(82)(83)(84)(85)(86)(87). Night shifts can lead to acute increases in glucose and insulin levels (88), although some studies report reduced insulin release in response to meals consumed during the night (89-91). Given that circadian disruption has been shown to independently adversely affect metabolism, and exposure to ALAN adversely impacts metabolism in animals [38], it is important to understand the extent to which circadian disruption contributes to the observed impact of sleep curtailment on metabolism[35]. **No previous studies of the metabolic impact of sleep restriction in humans have controlled for this additional exposure to ALAN, thus confounding the effects of sleep restriction with the effects of circadian disruption caused by extended exposure to ALAN.**

Seminal work by Spiegel and colleagues [10] demonstrated that 6 nights of sleep restriction to 4h per night caused impairments in glucose tolerance in otherwise healthy young men. Subsequent sleep restriction studies have replicated and expanded on these initial results [11-23,32], establishing a clear association between sleep restriction and disrupted glucose tolerance. Many of these studies employed rigorous methods for ensuring the participants remained awake throughout the sleep restriction [13-15,19,22,32], for recording sleep [13-17,19,32], and for assessing metabolism [11,13,14,16,17,19,20,22,32], although this was not true for all. In fact, in some cases participants were only provided test meals (and otherwise had uncontrolled diets [21]), participants were allowed to leave the laboratory during the day (so that wakefulness and adherence to the study diet were not controlled [10,16,21]), baseline sleep was scheduled at fixed times that may have induced difficulty sleeping [14-16], or objective evidence for adherence to the extended wake episodes was not documented (potentially missing the presence of brief naps in sleep-restricted individuals).

Importantly, none of the previous sleep restriction studies have controlled for longer exposure to ALAN when imposing an extended wake duration [10,11,13,15,16,20-22]. Individuals with restricted sleep, whether in the laboratory (31, 130, 131) or in normal life (65), are exposed to extended photoperiod and to altered meal timing, which can differentially entrain central and peripheral circadian oscillators (98, 126). Retinal exposure to ordinary indoor light can impact the human circadian system (132-137), and during sleep restriction additional light exposure occurs in the late evening and/or early morning, times when the circadian system is most sensitive to light (137-142). This additional nighttime light exposure may cause phase shifts (143) and melatonin suppression (136, 137). However, most sleep restriction studies have not assessed or controlled for such circadian disruptions. There is also evidence from animal studies that, in addition to light exposure, sleep loss can have a direct impact on neuronal activity in the master circadian pacemaker (144), which in turn can influence peripheral clocks in metabolic organs through neuronal and hormonal signals [reviewed in (43, 101)]. Thus, given that exposure to ALAN is known to be an endocrine disruptor and to profoundly disrupt circadian rhythms, and endocrine and circadian disruption can adversely affect metabolism [28,29], it is probable that endocrine and circadian disruption caused by the extended exposure to ALAN may contribute to the adverse metabolic effects

induced by chronic sleep restriction. We have therefore designed this study to be a direct comparison between sleep restriction with and without extended exposure to ALAN in order to distinguish the impact of sleep loss *per se* and sleep loss with extended photoperiod on glucose metabolism.

Determining whether endocrine and circadian disruption induced by ALAN contributes to the mechanism by which chronic sleep deficiency leads to the development of obesity, insulin resistance, and type 2 diabetes is important given the widespread prevalence of sleep deficiency in Americans of all ages. **By clarifying a potential mechanism by which sleep restriction impairs glucose metabolism, our findings will lay the groundwork for the development of novel treatments and countermeasures to mitigate the adverse metabolic effects of chronic sleep restriction.** If extended ALAN-induced endocrine and circadian disruption is one of the mechanisms by which sleep restriction impairs glucose metabolism, targeted countermeasures could be developed (e.g. eyeglasses that minimize the endocrine and circadian disruptions induced by ALAN by reducing exposure to short-wavelength artificial light, use of lamps with a lower color temperature to minimize exposure to short-wavelength artificial light during episodes of extended wakefulness, software to reduce exposure to short-wavelength light from light-emitting screens, etc).

## II. SPECIFIC AIMS

The goal of this project is to evaluate whether extended duration ALAN contributes to the adverse effects of sleep restriction on glucose metabolism. We plan to use a crossover design consisting of a 7-day baseline, 7-day sleep restriction (to 5h per night) with (LD 19:5) or without (LD 14:10) ALAN, 9-day washout, and another 7-day sleep restriction with or without ALAN (Figure 8). 20 healthy participants will be randomly assigned to receive ALAN in either the first or second exposure, balanced by age and sex. Specifically, we plan to:

1. Test the hypothesis that exposure to one week of sleep restriction with concurrent exposure to extended duration ALAN (LD 19:5) will induce greater impairment of insulin sensitivity than exposure to one week of sleep restriction without extended duration ALAN (LD 14:10). Insulin sensitivity (SI) will be assessed via an intravenous glucose tolerance test (ivGTT) before and after each week of exposure.
2. Test the hypothesis that exposure to one week of sleep restriction with concurrent exposure to extended duration ALAN (LD 19:5) will induce greater impairment of glucose tolerance than exposure to one week of sleep restriction without extended duration ALAN (LD 14:10). The 90-minute glucose area under the curve (AUC) will be assessed in response to a standardized meal both before and after each week of exposure.
3. Test the hypothesis that exposure to one week of sleep restriction with concurrent exposure to extended duration ALAN (LD 19:5) will reduce the duration of nocturnal melatonin secretion as compared to baseline more than exposure to one week of sleep restriction without extended duration ALAN (LD 14:10). The 24-h profile of melatonin secretion will be assessed during the lighting conditions that prevail throughout both sleep restriction conditions (i.e., 5h in darkness per night vs. 10h in darkness/near darkness per night). To determine the mechanism of this anticipated decrease in the duration of melatonin secretion (acute light-induced melatonin suppression vs. a reduction in the duration of the endogenous melatonin secretory profile), we will also measure the endogenous melatonin secretory profile on a ~24-hr recording on the day immediately after each week of intervention.
4. Exploratory Aim 4: Test the hypothesis that exposure to one week of sleep restriction with concurrent exposure to extended duration ALAN (LD 19:5) will lead to a greater reduction in the levels of long-chain highly unsaturated triglycerides than exposure to one week of sleep restriction without extended duration ALAN (LD 14:10). Plasma lipids will be assessed via mass spectrometry for a baseline and sleep-restricted sample from each participant in the above studies under ALAN and non-ALAN conditions. Because lower levels of long-chain highly unsaturated triglycerides are associated with a loss of insulin sensitivity [30], we will assess whether sleep restriction with ALAN leads to adverse changes in the levels of these triglyceride species that do not occur when sleep restriction is conducted without ALAN.
5. Exploratory Aim 5: test the hypothesis that exposure to one week of sleep restriction with concurrent exposure to extended duration ALAN (LD 19:5) will lead to a difference in the exhaled VOC profile compared with exposure to one week of sleep restriction without extended duration ALAN (LD 14:10).

6. Exploratory Aim 6: test the hypothesis that exposure to one week of sleep restriction with concurrent exposure to extended duration ALAN (LD 19:5) will lead to a change in the proteomic profile compared with exposure to one week of sleep restriction without extended duration ALAN (LD 14:10).
7. Exploratory Aim 7: test the hypothesis that the BodyTime assay will track changes in the melatonin profile and show a change in timing after exposure to one week of sleep restriction with concurrent exposure to extended duration ALAN (LD 19:5) compared to baseline.
8. Exploratory Aim 8: test the hypothesis that exposure to one week of sleep restriction will induce changes in objective human vocal parameters, both with and without extended duration ALAN.

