**Plasma lipidomics**. Profiling analysis involves giving primary consideration to a collective network of metabolites [levels of long-chain highly un-saturated lipids and short-chain, highly saturated lipids], and focusing on the determination of categorical differences between physiological states [baseline vs. after sleep restriction, with and without ALAN]. Our liquid chromatography-mass spectrometry (LC-MS) method enables separation of lipid classes as well as both qualitative and quantitative detection of >600 structurally identified individual lipids in biological samples. Data are acquired using high resolution full scan MS and high energy collisional dissociation MS/MS. The method was evaluated for efficient separation and detection in both positive and negative ionization mode using standards spanning 6 lipid classes. The approach is currently able to detect fatty acids (FA), sterols (ST), lysophosphocholines (Lyo-PC), phosphotidylcholines (PC), phosphotidylethanolamines (PE), lysophosphoethanolamines (Lyo-PE), phosphotidylglycerols (PG), sphinglipids (SL), diacylglycerols (DG), phosphotidylserines (PS), quinones such as ubiquinone, acyl carnitines, cholesterol esters, cholesterol sulfate, sulfatides, hexCers and other lipid subclasses. We will begin by generating lipidomic profiles of all samples, assess levels of individual lipids in baseline vs sleep restricted conditions (separately for each light/no light intervention at this phase) looking at both absolute and relative signal (ie., mass effect of lipids and relative occupation of total lipid pool). For the triglycerides, we will additionally assess the set Rhee et al. associated with diabetes risk [e.g., increased risk with TG 44:1; TG 46:1; TG 48:0; TG 48:1; TG 50:1; TG 52:1; decreased risk with TG 56:9, TG 58:10, TG 60:12]; we will then look at total carbons and total double bonds in each species in the triglyceride and phospholipid pools vs. the sleep restriction phenotypes. We will assess the within-person stability of each lipid within the baseline data itself. Finally, we will test the general hypothesis.

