For Specific Aim 3, we estimate that we will have 84% power ( $\alpha=0.0167$ , 2-sided paired t-test) with 20 subjects to detect a difference as small as 40 minutes (0.66 hrs) in the duration of melatonin secretion (1 hr with ALAN vs. 20 minutes without ALAN, assuming common SD=48 minutes). This should be more than adequate to detect the expected difference in melatonin secretion, given that we previously showed that evening exposure to room light shortened the duration of melatonin secretion by about 90 minutes (compared to dim lighting), even when participants remained in darkness for 8hrs/night during sleep[94]. Because participants in the current proposed

study will be exposed to room light for an extra 5 hrs/day in the sleep restriction with ALAN condition, we expect to see a more than 3-hour difference in the duration of melatonin secretion with and without ALAN.

For Exploratory Aim 4, we will consider two primary outcomes. We estimate that we have 85% power ( $\alpha=0.025$ , 2-sided paired-sample t-test) to detect an 20% difference in the change (25% with ALAN, SD=28% vs. 5% without ALAN, SD=6%) in levels of long-chain, highly unsaturated triglycerides, which have been associated with insulin sensitivity. Moreover, we estimate we will have 85% power to detect a difference as little as 11% in the change (5% with ALAN, SD=6% vs. 18% without ALAN, SD=19%) in levels of short-chain, highly saturated triglycerides, levels of which have been associated with increased diabetes risk.

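### Exploratory Aim 4 has no species-level test of ALAN against no ALAN; reading ALAN effects from separate baseline comparisons leaves the error rate uncontrolled and can miss the planned effect

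*Combined protocol and SAP*

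**What the plan says.** The documents hold two approaches to Exploratory Aim 4.

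**Class level.** The hypothesis in II. Specific Aims is a direct contrast: a "greater reduction in the levels of long-chain highly unsaturated triglycerides than exposure to one week of sleep restriction without extended duration ALAN (LD 14:10"). Under Sample size and power calculation the plan says "For Exploratory Aim 4, we will consider two primary outcomes", the long-chain highly unsaturated and the short-chain highly saturated triglycerides, and powers a paired comparison of the two changes: "85% power ( $\alpha=0.025$ , 2-sided paired-sample t-test").

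**Species level.** The same aim goes on to say "we will assess whether sleep restriction with ALAN leads to adverse changes in the levels of these triglyceride species that do not occur when" sleep is restricted without ALAN. The Plasma lipidomics paragraph in V. Study Procedures, which describes a method detecting more than 600 lipids, says the team will "assess levels of individual lipids in baseline vs sleep restricted conditions (separately for each light/no light intervention at this phase"), on absolute and relative signal. It then names a set of triglycerides linked to diabetes risk, and closes by saying the general hypothesis will be tested, without naming a model, an alpha or a unit of analysis.

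VI. Biostatistical analysis lists the outcomes whose changes are compared between conditions by paired test or mixed model. Lipids are not on that list.

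**The concern.** A change that is significant with ALAN and not significant without it does not show that the two changes differ. With 20 people, a non-significant change is weak evidence that nothing happened. The species-level wording looks for changes present in one condition and absent in the other, and the only comparison described for individual lipids is each condition against its own baseline. An analyst following that text could report species as ALAN-specific when sleep restriction moved them equally in both conditions. The same analyst could discard species that ALAN really affects, because a smaller change was also detectable without ALAN. Separating ALAN from sleep loss is the purpose of the aim, so both errors matter.

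**Working it through.** **Inputs from the plan**
- n = 20, each person measured in both conditions: "20 healthy participants will be randomly assigned to receive ALAN in either the first or second exposure".
- Long-chain class: "20% difference in the change (25% with ALAN, SD=28% vs. 5% without ALAN, SD=6"%), two-sided alpha 0.025.
- Short-chain class: "11% in the change (5% with ALAN, SD=6% vs. 18% without ALAN, SD=19"%). The two changes differ by 18 − 5 = 13, not 11; only the SDs are used here.

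**Assumptions (not in the plan)**
- Correlation rho between a person's two changes: 0 and 0.5 shown.
- Species-level alpha: 0.05, with 0.025 where stated.
- ALAN-only means: change with ALAN significant in the adverse direction, change without ALAN not significant.

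**Step 1. Reproduce the stated 85% (long-chain, direct test).** SD of the difference = sqrt(28² + 6² − 2·rho·28·6).
- rho = 0.5: sqrt(784 + 36 − 168) = 25.5; paired-t power for a 20-point difference = 84.7%.
- rho = 0: sqrt(820) = 28.6; power = 74.9%.

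The stated figure reproduces with rho of about 0.5.

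**Step 2. Same true change in both conditions, equal SDs, alpha 0.05.** At rho = 0 the ALAN-only rate is p × (1 − p), where p is the power of one within-condition test (with no change: 0.025 × 0.95). The rho = 0.5 column is simulated.

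| Standardized change | Power of one test | ALAN-only, rho 0 | ALAN-only, rho 0.5 |
|---|---|---|---|
| 0 | – | 0.025 × 0.95 = 2.4% | 2.0% |
| 0.5 | 56.5% | 0.565 × 0.435 = 24.6% | 17% |
| 0.65 | 78.7% | 0.787 × 0.213 = 16.8% | 12% |
| 1.0 | 98.9% | 0.989 × 0.011 = 1.1% | 1.0% |

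The direct paired test errs in 5% in total, 2.5% in the adverse direction, whatever the shared change.

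**Step 3. Same true change, the plan's own SDs.**
- Long-chain (28 with ALAN, 6 without): at most about 3.4% at alpha 0.05 and about 2.1% at 0.025. The ALAN test is the weaker of the two, so it is seldom the only significant one.
- Short-chain (6 with ALAN, 19 without), shared 5% change, alpha 0.025, rho = 0: 0.89 × (1 − 0.126) = 78%; 76% at rho = 0.5. It also exceeds 70% at alpha 0.05.

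**Step 4. The effect the plan expects (long-chain, alpha 0.025).** The change without ALAN (5%, SD 6%) is itself significant with 89.1% power, so ALAN-only can occur in at most 1 − 0.891 = 10.9% of trials. The ALAN change (25%, SD 28%) has 93.1% power, so at rho = 0 the rate is 0.931 × 0.109 = 10%; at rho = 0.5 it is about 8%. The direct test has 75% and 85% power.

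**The case against.** The strongest reply is that Aim 4 is already tested correctly. Its hypothesis is a direct contrast, its powered test is paired, and the power scenario allows a 5% change without ALAN, so the formal test does not depend on that change being absent. All of this stands. A reader might infer that separate within-condition testing is the formal analysis of Aim 4; the documents do not support that.

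The lipidomics step is also staged. The separate comparisons belong to an opening phase, the general hypothesis comes last, and no rule is written that attributes to ALAN whatever is significant in one condition only. The aim's sentence about species refers to the long-chain triglycerides, which receive a direct test as a class. These points stand too, and they make the problem conditional on how the text is applied. They do not fill the gap: the later step names no method, and no species receives a stated between-condition test.

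A reader might also infer that false ALAN findings would always far exceed the nominal rate. They would not: the rate is at or below 2.5% with no shared effect or a large one, and close to it under the long-chain SDs. Nor does counting within-condition tests across all lipids and both scales measure the problem. That counts false changes from baseline, not false ALAN effects, and when nothing changes the ALAN-only reading is no worse than the direct test.

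**Conclusion.** The concern holds as a gap at species level. The only comparison the plan describes for individual lipids is a poor basis for an ALAN conclusion, and nothing sets its error rate. If used as the rule, its false ALAN-only rate runs from about 1% to about 25% with equal SDs, depending on the shared effect and the correlation. It stays at or below about 3.4% with the long-chain SDs and can exceed 70% with the short-chain SDs. The loss of sensitivity rests on the plan's own long-chain figures plus a range for rho: 8 to 10% detection against 75 to 85%. The false-positive figures rest on an assumed species-level alpha and assumed shared effects. The aim is exploratory and the three primary outcomes are untouched, so this should be corrected but does not threaten the main results.

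**What to change.** 1. In Exploratory Aim 4, replace the phrase about changes that are absent without ALAN with wording for a greater change with ALAN than without it.
2. In Plasma lipidomics, state that every species-level ALAN conclusion rests on the within-person difference (change with ALAN minus change without), analysed by the paired test or mixed model already in VI. Biostatistical analysis, and add lipids to that section's list.
3. Name one scale in advance, absolute or relative, and control the false discovery rate across species on it, for example by Benjamini-Hochberg.
4. Label the separate baseline comparisons descriptive.

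The crossover already supplies both changes for each person, so no new data are needed. The cost is that fewer species will be called ALAN-specific.

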### III. SUBJECT SELECTION

A total of 20 healthy adults (20-40 years old) will be studied in this proposal. In order to obtain 20 people who meet all the study criteria and complete the 33-day inpatient study, we expect to enroll up to 100 people in the screening process for the study. Based on similar studies in the past, we anticipate that up to 25 individuals may be enrolled in the main study in order to have 20 complete the study. Approximately equal numbers of men and women will complete the study in each group.

Each potential participant will undergo an extensive screening procedure prior to participation in the study. The procedure begins with a telephone/online screening (to determine general medical suitability) and answering any questions potential participants may have about the study. If the original preliminary telephone/online screening questionnaire reveals no grounds for exclusion (see below), then potential participants are asked to come for an interview and physical screening. The physical screening includes a medical history, blood and urine tests, an ECG, and a physical examination by a physician or other qualified personnel (i.e physician assistant, certified nurse practitioner). Participants will also undergo psychological screening (see below), including questionnaires and a structured interview with a clinical psychologist. Finally, participants will be screened for sleep apnea and periodic limb movement disorder using a home sleep test.

We estimate that up to 10 individuals will inquire about the study for every 1 eventually studied, and that up to 5 individuals will begin the screening process for every 1 who successfully completes the screening and begins the study. We therefore plan to enroll up to 100 participants in the study in order to have 20 who pass all the screening and complete the 33-day study.

